4.3 Subject Recruitment and Screening

This study comprises several arms each of which is a specific disease involving the hand and upper extremity: trigger finger, De Quervain's disease, and tennis elbow. Subjects will be identified in the office visit for their hand and upper extremity complaints.

Equal gender distributions are expected in this study. Subjects will be 18 years of age or older. The hand and upper extremity disorders involved in the study are rarely if ever seen in patient population younger than 18 years of age. There will be no restriction to racial/ethnic background in terms of enrollment nor will any one particular racial/ethnic background will be sought out for enrollment over another. The diversity of the research subjects will be dependent on the diversity of patients seen in the hand offices of the investigators which is very broad as is the New York City Metropolitan area.

Patients will be enrolled from the private office of orthopaedic hand surgeons ([name] and [name]) and the resident hand clinic at NYU Hospital for Joint Diseases held at the 23rd street clinic.

There are no vulnerable subjects included in this study.

4.4 Subject Withdrawal

Patients can withdraw from the study at any time if they wish. Patients whose symptoms do not improve and are candidates for surgery can withdraw from the study and have surgery to correct their specific pathology (secondary endpoint). Patients enrolled in the study will be counseled regarding the likelihood of the injections working and will be given the opportunity for a second injection at 4 weeks from the time of the first injection if no significant symptoms have resolved. Ultimately it will be up to the patient whether they chose another injection or if they want to resort to a surgical intervention.

If patients experience adverse events they will be counseled regarding treatment alternatives for their pathology and any complications from the injection/medications will be treated appropriately. Because the study consists of a single injection at time point zero followed by serial examinations and completion of functional outcome surveys there is no need to stop treatment and withdraw patients from the study despite having an adverse event. The patient will simply not receive any more injections.

5 Study Drugs

5.1 **Ketorolac** (Investigational Agent)

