3.2 Primary Study Endpoints

The primary endpoint will be functional outcome scores at various follow-up time points using the quickDASH and EQ-5D questionnaire as well as a pain visual analog scale. The primary endpoint for the study would be resolution of symptoms or surgical intervention.

Primary endpoints will depend on the diagnosis of the patient. The following details what will be assessed at each follow-up visit after the initial injection:

- 1) Trigger finger group primary endpoint measures include the resolution of objective triggering and resolution of tenderness at the A1 pulley at subsequent follow-up visits. In addition, patients will be graded based on the Quinnell system to monitor for improvement: 0-normal movement of finger; 1-uneven movement; 2-active correctible locking of digit; 3-passively correctible locking; 4-fixed deformity (15). Patients will complete the quickDASH and EQ-5D questionnaires as well as a pain visual analog scale at each follow-up visit (27).
- 2) De Quervain's tenosynovitis group primary endpoint measures will include objective physical exam findings for the resolution of pain/tenderness over the 1st dorsal extensor compartment and the resolution of pain elicited during the Finkelstein test. In addition, patients will complete the quickDASH and EQ-5D questionnaires as well as a pain visual analog scale at each follow-up visit.
- 3) Lateral epicondylitis of the elbow group primary endpoint measures include the resolution of lateral elbow pain/tenderness over the extensor origin and the resolution of pain at the lateral epicondyle with resisted wrist extension during follow-up examinations. Patient grip strength will also be measured in this cohort using a hand dynamometer. Grip strength will be measured at each follow-up and the average of three tests with 20 second rests in between will be recorded. The contralateral side will also be measured for comparison. Lastly, patients will complete the quickDASH and EQ-5D questionnaires as well as a pain visual analog scale at each follow-up visit.

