3.4 Primary Safety Endpoints

Patients will follow-up after the first injection at 4-weeks, 8-weeks, 12-weeks, and 6 months post injection. During follow-up appointments patients in this study will be monitored based on history and physical exam for any side-effects associated with the administration of local soft tissue injections of dexamethasone or ketorolac.

Patients can withdraw from the study at any time if they wish. Patients whose symptoms do not improve and are candidates for surgery can withdraw from the study and have surgery to correct their specific pathology (secondary endpoint). Patients enrolled in the study will be counseled regarding the likelihood of

the injections working and will be given the opportunity for a second injection at 4 weeks from the time of the first injection if no significant symptoms have resolved. Ultimately it will be up to the patient whether they chose another injection or if they want to resort to a surgical intervention.

Patients who receive ketorolac by randomization as the therapeutic option will have an expected failure rate of approximately 30-50% based on clinical experience and literature review that shows the failure rate of dexamethasone (standard of care) on trigger fingers. The study population will be statistically analyzed biannually to determine if there is a significant difference in the rate of failures between the two groups, however a sizeable study population needs to be established before these conclusions can be drawn. If the rate of failure proves to be statistically significant between the ketorolac and dexamethasone group then the study will have to be ethically abandoned. This determination needs to take into consideration the pretreatment symptoms of the patient since patients who begin treatment with a severe trigger finger (quinnell score=4) have a different prognosis compared to patients who begin with a mild trigger finger (quinnell score=1).

4 Subject Selection and Withdrawal

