5.1.2 Treatment regimen

The proposed use of ketorolac in this study is outside of the FDA-approved indication and is the investigational agent in this study. Ketorolac will be administered as a peritendonous soft tissue injection of 1 mL of ketorolac (30mg/mL) and 0.5 mL (5mg) of 1% lidocaine.

Patients will be followed at the initial office visit, 4-weeks, 8-weeks, 12-weeks, and 6 months post injection to determine clinical response. A second injection can be given only once at each site of pathology if the patient desires due to no clinical response at the 4 or 8-week follow-up.

Patients will be divided into two groups. Group 1: 1 mL of dexamethasone sodium phosphate (4mg/mL) and 0.5 mL (5mg) of 1% lidocaine (*standard of care*). Group 2: 1 mL of ketorolac (30mg/mL) and 0.5 mL (5mg) of 1% lidocaine (*experimental group*). Patients will be followed at the initial visit, 4-weeks, 8-weeks, 12-weeks, and 6 months post injection to determine clinical response. A second injection can be given only once if the patient desires at the 4 or 8-week follow-up. These injections will be offered if the patient reports some improvement since the prior injection but still some persistent symptoms that have not completely resolved or if they had no response but would like another attempt to avoid surgery by receiving a second injection. The injection administered for the second time will correspond to the randomized group for the patient. Patients will not be compared separately if they receive one or two injections. However, with enough enrollment subgroup analysis can be performed to determine if receiving two injections significantly alters the outcome of the patient in regards to functional score improvement, surgery endpoint, or resolution of symptoms. The primary endpoint for the study would be resolution of symptoms or surgical intervention.

Patients receiving a second injection should be allowed to continue in the study. It is common practice for patients as part of the standard of care to receive multiple injections for hand and upper extremity pathology until these injections have been deemed non-therapeutic by the treating physician and surgical intervention is indicated.

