7.1 Sample Size Determination

The sample size as stated above was derived by a power analysis. A power analysis indicated that a total sample size of 200 patients randomized equally (1:1 randomization) to each treatment arm (i.e trigger finger, De Quervain's disease, and tennis elbow) without any blocking or stratification would provide 80% statistical power (alpha=.05, beta=0.20) to detect a 10% difference in mean DASH scores between cohorts assuming a common standard deviation of 25% (effect size = 10/25 = 0.4). To account for an estimated 30% loss to follow-up, we plan to enroll a total of 260 patients per treatment arm (i.e. trigger finger, De Quervain's disease, and tennis elbow). In total, there will be approximately 780 patients enrolled among all treatment arms, however we expect the trigger finger group to be the treatment arm that most rapidly enrolls patients.

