7.2 Statistical Methods

Statistics will be conducted by the statistician on faculty with the NYU Hospital for Joint Diseases. Primary analysis will consist of comparisons of the baseline functional scores (quickDASH and EQ5D). These scores will be analyzed and compared to subsequent scores at the various follow-ups (4-weeks, 8-weeks,

12-weeks, 6 months). In addition, changes in scores will also be analyzed between the baseline scores and the subsequent follow-ups. Statistical significance will be determined by p-values less than 0.05.

Secondary analysis will consist of physical exam findings and resolution of symptoms following injections as well as grip or pinch strength using pressure dynamometers to gage improved function following injections as well. In addition, observation of side effects will also be included in the secondary analysis.

8 Safety and Adverse Events

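### Non-improving patients may leave the study for surgery, and nothing secures their later scores, so the primary quickDASH and EQ-5D comparison can lose data because the injection failed

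*Combined protocol and SAP*

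**What the plan says.** Section 4.4 ties one exit route to lack of response: "Patients whose symptoms do not improve and are candidates for surgery can withdraw from the study and have surgery". Section 3.4 has the same rule and labels the surgery an endpoint: such patients "can withdraw from the study and have surgery to correct their specific pathology (secondary endpoint"). A second injection is offered at 4 weeks, but the choice is the patient's: "Ultimately it will be up to the patient whether they chose another injection or if they want to resort to a surgical intervention".

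Visits are at 4, 8 and 12 weeks and 6 months. In section 3.2, under trigger finger, "Patients will complete the quickDASH and EQ-5D questionnaires as well as a pain visual analog scale at each follow-up visit"; the other two diagnoses have the same requirement. Section 7.2 makes quickDASH and EQ-5D the primary analysis: "These scores will be analyzed and compared to subsequent scores at the various follow-ups", the last at 6 months. It names no analysis population, no missing-data method and no treatment of scores taken after surgery.

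The surgery itself is counted. Section 5.1.2 states: "The primary endpoint for the study would be resolution of symptoms or surgical intervention". Sections 3.4, 4.4 and 10.1 call it a secondary endpoint. Section 3.4 also compares failure rates twice a year.

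Three other places touch on lost data:

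- Section 7.1 enlarges the sample: "To account for an estimated 30% loss to follow-up, we plan to enroll a total of 260 patients per treatment arm". It does not say whether surgical exits are part of the 30%.
- Section 9.3 requires an explanation for missing data, which is a record-keeping duty.
- Section 10.1 keeps drop-outs under observation at their usual appointments until discharge, without mentioning scores.

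Sections 1.6.1 and 4.4 also disagree on adverse events. The first withdraws every patient who has one. The second says withdrawal is unnecessary and only further injections stop.

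**The concern.** Leaving by this route depends on the outcome, because only patients who have not improved are offered it. Those who remain to give scores at 8 weeks, 12 weeks and 6 months are then a selected group with too many successes. If the selection is the same in both arms it cancels. If the arms differ in how many patients fail, or in how many failures leave, it does not cancel, and the difference in mean scores is distorted.

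This matters because the objective in section 2 is to learn whether ketorolac relieves symptoms as well as the steroid or better, and the sample size in 7.1 rests on a DASH score difference. Enrolling more patients restores precision but does not remove selection. If scores are in fact taken after surgery, a different question arises: a good surgical result enters the average as if it followed from the injection, and 7.2 does not say whether that is intended.

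**Working it through.** **The plan's own figure.** Section 7.1 uses a difference of 10, SD 25, alpha 0.05 (taken as two-sided) and 80% power. The normal approximation gives 2 × (1.96 + 0.842)² × (25/10)² ≈ 98.1, so 99 per drug and 198 in total. The t test gives 99.1, so 100 per drug. The stated 200 reproduces, and it is not in dispute here.

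**Inputs for the illustration.** Only the range comes from the documents: section 3.4 gives ketorolac an "expected failure rate of approximately 30-50% based on clinical experience" and literature. The rest is assumed: 30% failure in the better arm and 50% in the worse (the two ends of that range), failures scoring 20 points worse than successes, and a share q of failures leaving for surgery with no later scores.

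**True difference.** (0.50 − 0.30) × 20 = 4.0 points.

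**Failures among those who remain.** With failure rate p, the share is p(1 − q)/(1 − qp).

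| q | Better arm (p = 0.30) | Worse arm (p = 0.50) |
|---|---|---|
| 0.25 | 0.225/0.925 = 0.243 | 0.375/0.875 = 0.429 |
| 0.50 | 0.150/0.850 = 0.176 | 0.250/0.750 = 0.333 |
| 0.75 | 0.075/0.775 = 0.097 | 0.125/0.625 = 0.200 |

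**Observed difference** = 20 × (worse-arm share − better-arm share), for each pair of exit shares:

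| | Worse arm q = 0.25 | Worse arm q = 0.50 | Worse arm q = 0.75 |
|---|---|---|---|
| Better arm q = 0.25 | 3.7 | 1.8 | −0.9 |
| Better arm q = 0.50 | 5.0 | 3.1 | 0.5 |
| Better arm q = 0.75 | 6.6 | 4.7 | 2.1 |

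**Equal shares (the diagonal).** The ratio of observed to true difference is (1 − q)/[(1 − 0.30q)(1 − 0.50q)] = 0.927, 0.784 and 0.516. These are losses of 7%, 22% and 48%, whatever the score gap. For general failure rates the ratio is below 1 whenever the two rates sum to no more than 1, which holds for any pair within 30-50%.

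**Unequal shares (off the diagonal).** The difference can shrink, reverse or grow.

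**Equal failure, unequal exit.** With p = 0.40 in both arms (the midpoint of the range) and q = 0.25 and 0.75, the shares are 0.30/0.90 = 0.333 and 0.10/0.70 = 0.143. A true difference of zero then reads 0.190 × 20 = 3.8 points. With equal p and equal q the bias is zero.

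**Scores kept after surgery.** If surgery fully resolves symptoms, equal shares leave and scores are used as observed, the difference is 4.0 × (1 − q) = 3.0, 2.0 and 1.0 points.

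**Scale.** With 30% lost, 260 leaves 182, or 91 per drug. The standard error of the difference is 25 × √(2/91) = 3.7 points.

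**The case against.** The strongest reply has four parts.

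- **The 30-50% range is one range.** Section 3.4 gives it for ketorolac, carried over from dexamethasone in trigger finger. A reader might infer from the illustration that the protocol expects 30% in one arm and 50% in the other. It does not. If failure is similar and exit equal, as blinding makes plausible, there is no bias. This stands, and it is why the figures are an illustration only.
- **A large imbalance would probably show elsewhere.** Surgery is an endpoint in its own right, and section 3.4 would abandon the study on a significant difference in failure rates. At 30% against 50%, a single two-sided 0.05 comparison has about 79% power with 91 per arm and 91% with 130. This limits the harm of a misleading score result but does not repair the scores.
- **The distortion can be small against the noise.** The equal-share losses are 0.3, 0.9 and 1.9 points, against a standard error of 3.7. This also stands, although several unequal-share cases exceed 2 points.
- **Loss is possible, not prescribed.** Patients may withdraw but need not, drop-outs are still seen, and section 5.1.2 describes repeat injections before surgery, so exit before 8 weeks is the earliest case rather than the usual one. A reader might infer that all scores stop at surgery. The documents do not say that; they leave it open. The Data and Safety Monitoring Plan cited in 8.4 and 10.1 was not available and might say more about follow-up, but the analysis rule belongs in 7.2.

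**Conclusion.** The point holds as a cheap improvement. Following the plan as written can lose primary scores after the 4-week visit because the injection failed, and no section says how such scores, or scores taken after surgery, are to be used. The resulting bias has unknown size and direction. It is towards zero if equal shares of failures leave in each arm (given failure rates within 30-50%), in either direction if the shares differ, and zero if failure and exit rates are equal. The range of −0.9 to 6.6 points around a true 4.0 rests on assumed failure rates, exit shares and a 20-point gap, and is no forecast.

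Two stronger readings are tempting. One is that the plan must favour a finding of no difference, and so ketorolac. That needs equal exit shares, which the documents neither state nor rule out. The other is that surgical exits cost a definite amount of power. No exit rate is given, and 7.1 does not say whether the 30% already includes them, so no figure can be supported.

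**What to change.** **Sections 3.4 and 4.4.** State that surgery at the injected site may take place at any time, is recorded with its date as an endpoint and does not end participation. quickDASH, EQ-5D and pain VAS continue at the remaining scheduled times to 6 months, by mail or phone if needed. Withdrawal is reserved for withdrawn consent.

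**Section 7.2.** Analyse all randomised patients in their assigned group and report surgeries by arm. Pre-specify two score analyses: one using scores as observed regardless of surgery, one counting surgery as treatment failure from its date. The sponsor should choose the main one in advance. The as-observed analysis keeps the mean comparison that 7.1 powers. A rank-based failure analysis would not, and if chosen as main would need its own power statement. Because surgery is partly the patient's choice, counting every operation as failure is debatable, which is why both are needed. Patients with several injected sites (4.1, 5.5) need a line on how surgery at one site affects scores recorded for another.

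**Section 1.6.1.** Align it with 4.4, so that an adverse event stops further injections but not follow-up.

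**Cost.** Protocol wording, a matching consent sentence, a few remote questionnaires and one extra analysis. Patients keep the same freedom to have surgery.

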5.1.1 Description

Ketorolac is a nonsteroidal anti-inflammatory drug (NSAID). The approved indication for Ketorolac is for the short-term (≤5 days) management of moderately severe, acute pain that requires analgesia at the opioid level, usually in a postoperative setting. It is highly protein bound (99%) and is largely metabolized by the liver. It is indicated for short-term management of severe acute pain as intravenous or intramuscular injections.

In its approved indication it is contraindicated for those with renal impairment, active peptic ulcer disease, pregnant or nursing females, individuals with NSAID hypersensitivity, or individuals at high risk for bleeding/clotting disorders.

5.1.2 Treatment regimen

The proposed use of ketorolac in this study is outside of the FDA-approved indication and is the investigational agent in this study. Ketorolac will be administered as a peritendonous soft tissue injection of 1 mL of ketorolac (30mg/mL) and 0.5 mL (5mg) of 1% lidocaine.

Patients will be followed at the initial office visit, 4-weeks, 8-weeks, 12-weeks, and 6 months post injection to determine clinical response. A second injection can be given only once at each site of pathology if the patient desires due to no clinical response at the 4 or 8-week follow-up.

Patients will be divided into two groups. Group 1: 1 mL of dexamethasone sodium phosphate (4mg/mL) and 0.5 mL (5mg) of 1% lidocaine (*standard of care*). Group 2: 1 mL of ketorolac (30mg/mL) and 0.5 mL (5mg) of 1% lidocaine (*experimental group*). Patients will be followed at the initial visit, 4-weeks, 8-weeks, 12-weeks, and 6 months post injection to determine clinical response. A second injection can be given only once if the patient desires at the 4 or 8-week follow-up. These injections will be offered if the patient reports some improvement since the prior injection but still some persistent symptoms that have not completely resolved or if they had no response but would like another attempt to avoid surgery by receiving a second injection. The injection administered for the second time will correspond to the randomized group for the patient. Patients will not be compared separately if they receive one or two injections. However, with enough enrollment subgroup analysis can be performed to determine if receiving two injections significantly alters the outcome of the patient in regards to functional score improvement, surgery endpoint, or resolution of symptoms. The primary endpoint for the study would be resolution of symptoms or surgical intervention.

Patients receiving a second injection should be allowed to continue in the study. It is common practice for patients as part of the standard of care to receive multiple injections for hand and upper extremity pathology until these injections have been deemed non-therapeutic by the treating physician and surgical intervention is indicated.

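### The optional one-versus-two-injection comparison is confounded by early response and cannot show what a second injection does

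*Combined protocol and SAP*

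**What the plan says.** Section 5.1.2 pools patients with one and two injections in the main comparison. It then adds that, if enrolment is large enough, "subgroup analysis can be performed to determine if receiving two injections significantly alters the outcome of the patient in regards to functional score improvement", and names surgery and resolution of symptoms as further outcomes for the same question.

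The same section sets out who gets the second injection. At week 4 or 8 it is offered to patients who have improved in part but still have symptoms, or "if they had no response but would like another attempt to avoid surgery by receiving a second injection". It is given only if the patient wants it, and the drug is the one first allocated. Section 5.5 randomises the drug; nothing randomises the number of injections.

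Section 7.2 sets the general rule, "Statistical significance will be determined by p-values less than 0.05", but does not list this analysis. No section gives an adjustment, a fixed starting visit or a caution about selection.

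The condition for a second injection is also worded differently in different places:

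- The synopsis requires the lack of a major response at week 4 or 8.
- Sections 3.4 and 4.4 mention week 4 only, where no significant symptoms have resolved.
- Section 5.2.2 and the opening part of section 5.1.2 require no clinical response.
- The later part of section 5.1.2 also admits partial responders.

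**The concern.** Whether a patient has one or two injections is settled after randomisation, by how the patient did after the first injection and by what the patient then chose. Patients who did well early have one injection by rule. The two-injection group consists of patients who still had symptoms. A difference between these groups mixes any effect of the second injection with the prognosis that led to it, and a significance test cannot separate the two.

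Section 5.1.2 describes repeat injection as common standard practice. A spurious result on it could be read as evidence about routine care. The protocol's only condition, more enrolment, does not help: a larger sample leaves the bias the same size and makes it more likely to reach significance.

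**Working it through.** **The plan's own figure.** Section 7.1 uses a difference of 10, an SD of 25, alpha 0.05 and 80% power. Two-sided, n per arm = 2 × (1.96 + 0.842)² × (25/10)² = 98.1, so 99 per arm and 198 in total. This agrees with the stated 200 per condition. The 10 points and the SD of 25 serve as the yardstick below.

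**Common set-up.** The true effect of the second injection is set to zero.

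- From the documents: SD 25; N = 200 in one condition, both drugs pooled.
- Assumed: f, the fraction re-injected, 0.3–0.5. The range is borrowed from section 3.4, where ketorolac patients "will have an expected failure rate of approximately 30-50% based on clinical experience and literature review". That is a failure rate drawn from dexamethasone in trigger finger, not a re-injection rate.
- Assumed: ρ, the correlation between week-4 and 6-month scores, 0.3–0.7.
- Assumed: s, how strongly re-injection follows the week-4 score. At s = 1, exactly the worst fraction f is re-injected.

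**Follow-up score.** False gap = 25 × ρ × s × k, with k = φ(z)/[f(1−f)]. For f = 0.5, k = 0.399/0.25 = 1.596. For f = 0.3, k = 0.348/0.21 = 1.656.

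| s | ρ = 0.3 | ρ = 0.5 | ρ = 0.7 | p < 0.05, N = 200 |
|---|---|---|---|---|
| 1 | 12.0–12.4 | 19.9–20.7 | 27.9–29.0 | 90–100% |
| 0.5 | 6.0–6.2 | 10.0–10.3 | 14.0–14.5 | 36–98% |
| 0.3 | 3.6–3.7 | 6.0–6.2 | 8.4–8.7 | 16–66% |

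Example for the lowest rate (s = 0.3, ρ = 0.3, f = 0.3): gap 3.73; standard error 25 × √(1/60 + 1/140) = 3.86; ratio 0.97; rejection about 16%. With 182 patients (260 × 0.70), simulation put this low end at 14%. A false gap of 10 points needs ρ × s = 10/(25k), which is 0.24–0.25.

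**Change from baseline.** Section 5.1.2 speaks of improvement, so the change score matters too. Write r₀₄, r₄₆ and r₀₆ for the correlations among baseline, week 4 and 6 months.

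- Selection on the week-4 level: gap = 25 × (r₄₆ − r₀₄) × k. It is 0 if all correlations are equal. With r₀₄ = 0.4 and r₄₆ = 0.6 it is about 8; with 0.3 and 0.7 it is 16–17.
- Selection on the week-4 change: gap = 25 × k × (1 + r₄₆ − r₀₄ − r₀₆)/√(2 − 2r₀₄). Over the correlations tried, this gave 15.5–38.5 points at s = 1 and 7.7–19 at s = 0.5.

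**Resolution.** Here f is the fraction unresolved early, q the share of them who take the second injection, and g their later resolution rate, the same with or without it. Early resolution is taken to last; recurrence would narrow the gap. The one-injection group resolves at [(1−f) + f(1−q)g]/(1−fq) and the two-injection group at g. The difference is (1−f)(1−g)/(1−fq).

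- f = 0.5, q = 0.5, g = 0.4: 0.5 × 0.6/0.75 = 40 percentage points.
- f = 0.3, q = 0.8, g = 0.2: 0.7 × 0.8/0.76 = 74 percentage points.
- If every decliner goes to surgery instead (f = 0.5, q = 0.5, g = 0.4): 0.5/0.75 = 67% against 40%.

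**Surgery.** Suppose every non-responder who declines goes to surgery. The one-injection surgery rate is then f(1−q)/(1−fq). With f = 0.5 and q = 0.3 it is 0.35/0.85 = 41%. Against an assumed 20% to 60% in the two-injection group, the difference can go either way.

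**Adjustment.** In simulations where re-injection depended only on the week-4 score, adjusting for that score left a false difference of −0.3 to +0.2 points and a false-positive rate of 4.6–5.8%.

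**The case against.** The strongest reply is that this analysis is optional. Section 5.1.2 first says that the two kinds of patient are not compared separately, the subgroup sentence is permissive and conditional on enrolment, and section 7.2 omits it. That stands. A reader might infer that the trial's main result is at risk. The documents do not support this, because the dexamethasone–ketorolac comparison rests on the randomised drug, whatever the number of injections.

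A reader might also infer that a false significant result is nearly certain; with 182 patients and full selection, simulation gives 87–100%. That figure requires the worst scorers to be exactly those re-injected. The documents describe looser selection: partial improvers may be offered the injection, the patient decides, and section 4.4 lets non-improvers leave for surgery. At weaker selection the rates fall well short of certainty.

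Nor do the documents support the inference that the bias always makes a second injection look harmful. Non-responders who go straight to surgery count as one-injection patients if they stay in the analysis, so the surgery result can point either way. For change from baseline the bias can be nil.

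Finally, no method is specified, so an adjusted analysis is not ruled out. It could work, but only if the recorded score captures everything behind the offer and the choice. Patient preference is part of that rule, so this cannot be assumed. The objection limits the size, direction and weight of the point. It does not rescue the claim that the comparison can determine the effect.

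**Conclusion.** The point holds as a flaw in an optional analysis. That the comparison is confounded follows from the offer rule alone and needs no assumed number. With a second injection that does nothing:

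- Resolution still favours the one-injection group, by 40–74 percentage points on the main assumptions used.
- The false gap in follow-up scores is about 12–29, 6–14.5 or 3.6–8.7 points as selection weakens from 1 to 0.5 to 0.3, with false-positive rates from roughly 15% to 100%.
- The gap in change from baseline runs from nil to large.
- The direction for surgery is not fixed.

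Only the SD and N come from the protocol. The re-injected fraction, correlation, selection strength, uptake and later resolution rate are assumptions. Confidence is high that the analysis cannot answer its question, and much lower about the size of the error.

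**What to change.** Remove from section 5.1.2 the statement that this analysis can determine whether a second injection alters outcome. In its place:

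1. Compare the randomised drugs on the proportion receiving a second injection and the proportion going to surgery. Read the two together, since a patient who moves early to surgery has no second injection. First reconcile the status of surgery, which sections 3.2, 5.1.2 and 5.4 place within the primary endpoint and sections 3.4, 4.4 and 10.1 call secondary. State whether the unit is the patient or the site, because section 4.1 allows up to three sites to be injected at one visit and section 5.5 tracks each site separately.
2. Report outcomes after a second injection descriptively. Any one-versus-two comparison should adjust for the score at the visit where the injection was offered, and be labelled exploratory and non-causal.
3. Reconcile the differing conditions for a second injection in the synopsis and sections 3.4, 4.4, 5.1.2 and 5.2.2, since they define who is selected.

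The cost is protocol and analysis-plan wording; the trial already generates the data needed. The protocol gives up a causal answer on repeat injection that its design cannot provide.
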